Each of the two population cohorts (South Asian and White British) has four sub-groups (clinically uninfected subjects, asymptomatic/mild, symptomatic moderate/severe, and recovered). After patient information sheets and consent, then oral health questionnaires (5mins), SWMF samples (5-15 mins), oral health (periodontal) examination (10 mins), and blood via venesection (5 mins). Patients will chew on a pellet of wax until approximately 4ml SWMF is recovered by drooling into sterile universal containers (between 5 and 10 minutes normally) after which the chewed wax will be wrapped in gauze and disposed with other clinical waste in adherence to infection control procedures. Blood samples may be taken before, during or after the SWMF collection. Repeat blood and stimulated SWMF will be taken at approximately 2 weeks, 4 weeks and 12 weeks after baseline for those participants willing to take part in the sequential studies. Oral examination and partial mouth recording will not be repeated unless any material change in oral condition is evident.

Uninfected subjects will be further defined as those who do not show antibodies to nuclear capsid protein antigens. The presence of such antibodies would indicate exposure to SARS-CoV2 rather than immunisation, and would be classified as asymptomatic if no history of symptoms.

Number of samples: With South Asian and White British participants, there will be up to 100 patient samples in each of the four sub-groups (uninfected subjects, asymptomatic/mild and moderate/severe disease, and recovered.). All will be assayed for immunological parameters, and the first 50 in each group for microbiome analysis, with the remainder stored for future analysis. The first 50 participants in each group will be invited to provide sequential samples.

Times of samples: There will be repeat samples of SWMF and blood at approximately 2, 4 and 12 weeks. Those SWMF at 4 weeks will be analysed for the microbiome in addition to the immunology (see table 1).

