Choice of time points: Mucosal immunological responses have a different and often shorter time frames than systemic responses. The 2 week post infection or post vaccination time point as well as the 4 week time point is to determine whether a response has been generated, and indicate possible kinetics of the mucosal response in comparison with systemic (serum) responses. The 12-week sampling point was selected as optimal to indicate longevity of any mucosal response, and any differential between a possible protective response of longer duration from a response of shorter duration.

Handling of samples: After collection, samples for GSTT haematology (Viapath) and blood glucose (if results not already available) will be sent to GSTT haematology. Study pseudoanonymised samples will be transported to the Centre for Host-Microbiome Interactions (CHMI) laboratories in Guy's Tower by the clinical research dentist. SWMF will be transported on ice. All samples will be subject to current infection control measures and containers pre-labelled. In the lab, SWMF samples will be centrifuged and immune factors including cytokines and anti-SARS-CoV2 antibodies assayed in the supernatant, whilst cellular factors determined in reconstituted pellet. DNA extraction for the microbiome studies will be performed on the saliva pellet. Peripheral blood T cell phenotypes will be assayed in the supernatant from plasma. Recruitment: Patients identified by the clinical team will be recruited by a clinical research assistant and consented. Uninfected subjects and ambulant patients will be recruited within Guys

and St Thomas' Hospital sites, from KCL sites and for General Medical Practice PIC (participant identification centre) sites. Symptomatic patients will be recruited from within outpatients or on the wards. From each subject, basic medical data will be collected and an oral health questionnaire applied, followed by SWMF, an oral examination and blood samples as above.

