Asymptomatic/mild subjects will be recruited from those identified as positive for SARS-CoV2 carriage in routine testing at KCL or GSTT. In both cases local staff will inform them about the trial and give out a patient information sheet. A medical history will be taken from those who consent to take part in the research

Symptomatic moderate/severe patients will be recruited within Guys and St Thomas Hospital, mainly in conjunction with the GSTT COVID infection teams. Patients will be recruited from those admitted or planned to be admitted to GSTT with a recent onset (≤ 21 days) of symptoms of COVID-19 and a confirmed positive nasal/nasopharyngeal PCR test for SARS-CoV-2. They will be identified and approached by the clinical staff caring for them on the wards who will discuss the trial in outline and offer the PIL. Should the patient wish to consider participation after reading the PIL, the clinical research dentist (summoned by clinical ward staff) will obtain signatures of consent.

Recovered participants will be patients who have had COVID and fulfil the inclusion criteria. They will have either been discharged from GSTT or be attending either the post-COVID or ICU follow-up outpatient clinics and will be sent letters of invitation to participate. They will also be recruited from participating GP PIC sites, KCL sites and GSTT sites

Number of subjects	Subject selection
Group 1. SA1, BW1 Uninfected Subjects (n=100 each)	Uninfected subjects, both South Asian and White British will be recruited by advertisement within KCL or social media, from non-COVID in-patients or outpatients or attending A&E at GSTT and at SARS-CoV2 antigen testing centres and vaccination centres and at PIC sites. They will be furnished with the participant information leaflet and invited to take part in the study. After obtaining informed consent, oral examination, oral & general health questionnaires and samples of blood and stimulated whole mouth fluid (SWMF) (see below) will be taken either on the wards (inpatients), A&E or at the department of Oral Medicine at Guys Hospital
Group SA1v, BW1v (n=50)	In a subset of uninfected subjects from those attending for vaccination or volunteers, blood and SWMF will be taken 2 weeks after the first vaccination and 2 weeks after the second vaccination for immunology and microbiome analysis.

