3.1 Inclusion Criteria

Inclusion criteria
	
 • South Asian and White British persons and those diagnosed with symptomatic or asymptomatic COVID-19 infection, or recovered from COVID infection or previously uninfected. • Aged 18 or over. Able to understand and consent. • For inpatient groups: Confirmed COVID-19 positivity, symptoms and symptom onset within the past 21 days; Be recently (within 7 days) hospitalised with COVID-19 disease; Have COVID-19 disease proven by PCR testing for SARS-CoV-2 within the last 21 days; • Uninfected subjects: no history of COVID-19; not vaccinated; (negative for anti-SARS-CoV2 nucleoprotein antibodies at lab)
---------------------------	--

	
 • Recovered groups: Have had COVID-19 disease proven by PCR testing for SARS-CoV-2. • Those willing to participate on a single occasion but unwilling to participate with longitudinal samples will not be excluded. • Smoking, obesity, diabetes, heart disease, antibiotics or treatment related to COVID is not excluded.
--	--

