4.5 Follow up visits

Participants will be reviewed as per schedule above (2.3) and repeat samples of SWMF and blood taken. The oral health questionnaire and the whole mouth examination will not be repeated, unless there are major changes in the clinical condition. Participants will be given a window of +_ 5 days for scheduling appointments.

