5.5 Data Recording/Reporting

The data obtained during this study will comply with community standards for research data. King's College London aspires to ISO 27001 standards for data security. All hard copy data and link codes will be kept in a GSTT locked and secure filing cabinet in a locked room based in the PI's office Department of Periodontology, Faculty of Dentistry, Oral and Craniofacial Sciences in Guys Dental Hospital. Additional back up of link codes will be stored on secure GSTT storage. All pseudoanonymised electronic data will be held on KCL firewalled computers, subject to KCL standard audits. In addition, data will be stored at KCL high performance computers with weekly backup program. Data will be recorded by a dedicated technician who will be HTA trained.

Data analyses:

The immunological markers will be compared between the healthy controls, asymptomatic and symptomatic COVID-19 patients using Mean, Median and non-parametric tests like Anova and Mann-Whitney rank sum tests. The immunological markers in the blood and SWMF will be compared and analysed at various time points of the disease progression. The key immunological parameters will be compared with the oral microbiome data to identify key biomarkers that may be indicative of the pathogenesis of the disease. These parameters will also be compared between the South Asian and the British-Caucasian population recruited in the UK. At the conclusion of the study, all the above analyses of the immunological and oral microbiome parameters will be compared among the age-matched and disease-matched participants in the UK and a collaborative, parallel study performed by collaborators in Chennai, India.

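### The early sample is justified as two weeks after infection but scheduled from enrolment, and the CRF list has no onset date, so severity contrasts and trajectories can be confounded by time since infection

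*Protocol*

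**What the plan says.** **Rationale.** Under its heading on the choice of time points, Protocol section 2.2 says: "The 2 week post infection or post vaccination time point as well as the 4 week time point is to determine" whether a response was generated and what its kinetics might be, compared with serum.

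**Schedule.** Earlier in section 2.2: "Repeat blood and stimulated SWMF will be taken at approximately 2 weeks, 4 weeks and 12 weeks after baseline". Table 1 (section 2.3) gives the first repeat as 10–14 days, and section 4.5 adds: "Participants will be given a window of +_ 5 days for scheduling appointments". Only the vaccination subset is timed from its own event, two weeks after each dose.

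**Entry relative to infection.** Section 3 recruits moderate/severe patients "admitted or planned to be admitted to GSTT with a recent onset (≤ 21 days) of symptoms of COVID-19". Section 3.1 repeats the limit for inpatients only: "For inpatient groups: Confirmed COVID-19 positivity, symptoms and symptom onset within the past 21 days". For recovered participants it asks only: "Have had COVID-19 disease proven by PCR testing for SARS-CoV-2". No limit is stated for asymptomatic/mild participants who are not inpatients. Sections 2.2 and 3 also move would-be uninfected volunteers with nucleocapsid antibody and no symptom history into the asymptomatic category.

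**Use of the data.** The primary endpoint (section 2.1) includes marker differences by COVID severity. Section 5.1 promises to identify changes as the disease moves between its viral, immunological and later phases. Section 5.5 says: "The immunological markers in the blood and SWMF will be compared and analysed at various time points of the disease progression".

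**Recording.** The CRF list in section 10 names the date and time of sample collection. It does not name a date of onset, first positive test or index infection.

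**The concern.** The two parts of section 2.2 use different time origins. They differ by however long the participant had been infected at enrolment, and that lag varies from person to person. A visit number is therefore not a disease time.

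This matters because the protocol's hypotheses are about time. Its model figure has an antigen peak lasting 5–7 days, neutralising antibody potentially appearing after about a week, and prolonged cytokine responses in severe disease. A marker difference between severity groups could then reflect when in the illness each group was sampled as well as how ill it was. The groups reach the study differently: severe cases mainly through admission, mild ones through routine testing, testing centres, A&E or an incidental positive on a ward. A systematic difference in lag is plausible. If the date is not collected, no later analysis plan can adjust for it.

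A secondary matter is that the protocol promises visit-to-visit and blood-versus-SWMF comparisons but names no paired or repeated-measures method.

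**Working it through.** **Which groups have the early visit.** Table 1's sequential totals reproduce at 50 per sampled group: 4 × 50 = 200 at 10–14 days, 8 × 50 = 400 at 4 weeks, 6 × 50 = 300 at 12 weeks. In Table 1 the 10–14 day sample belongs to the two asymptomatic/mild and two moderate/severe groups; recovered groups have none.

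**Days since onset.** Inputs: lag L = 0 to 21 days (sections 3 and 3.1); visit at 10–14, 28 or 84 days after baseline (Table 1); window ±5 days (section 4.5). Earliest day = 0 + lower visit day (− 5); latest day = 21 + upper visit day (+ 5).

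| Sample | Without window | With window |
|---|---|---|
| Baseline | 0 to 21 | – |
| 2-week | 10 to 21+14 = 35 | 5 to 40 |
| 4-week | 28 to 21+28 = 49 | 23 to 54 |
| 12-week | 84 to 21+84 = 105 | 79 to 110 |

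The 2-week and 4-week samples overlap between patients on days 28–35, or 23–40 with the window. Within one patient they do not: the 2-week sample ends at L + 19 and the 4-week sample starts at L + 23.

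**Example.** A patient enrolled on day 14 gives the 2-week sample on day 14 + 14 = 28. A patient enrolled on day 0 gives the 4-week sample on day 0 + 28 = 28. Different visit labels, same disease time.

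**Against the protocol's own model.** The permitted lag is 21/7 = 3 to 21/5 = 4.2 times the virological phase, so baseline can mix early samples with late ones.

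These ranges apply where the 21-day limit applies. Elsewhere no upper bound can be calculated.

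**Secondary: cost of ignoring pairing.** The protocol gives no effect size or within-person correlation, so both are assumed: a 0.5 SD shift, correlation 0.3 to 0.7, normal data, two-sided 5% level, 4,000 simulated studies per setting.

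| n | Correlation | Mann–Whitney power | Signed-rank power |
|---|---|---|---|
| 30 | 0.3 / 0.5 / 0.7 | 0.45 / 0.44 / 0.42 | 0.60 / 0.73 / 0.91 |
| 50 | 0.3 / 0.5 / 0.7 | 0.71 / 0.74 / 0.79 | 0.82 / 0.93 / 0.99 |

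With no true shift, Mann–Whitney on paired visits rejects in about 2%, 0.7% and 0.1–0.2% of studies at these correlations. It is conservative.

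**The case against.** Several counter-arguments have force.

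- **The ranges are extremes.** No lag distribution is given, and the lower limit of day 5 takes the window below Table 1's own 10 days. That is fair, which is why the figures without the window are shown; they still overlap.
- **Onset is partly recoverable.** Inpatient eligibility requires onset and PCR dates to be checked, and medical history is recorded. This stands for inpatients. It does not cover non-inpatient or recovered participants, and an unnamed field may be filled unevenly.
- **The model is a hypothesis.** Antibody timing in the figure is tentative, and the Introduction cites responses within 2–3 days. Either way, a baseline spread over 0–21 days can straddle the response.
- **The scope is limited.** The post-vaccination half of the quoted sentence is sound, and the ethnic comparison is affected only if lag differs by ethnicity, for which there is no evidence here.

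A reader might also infer that repeated samples will receive only independent-sample tests, and that within-person change cannot be validly estimated. The document does not support this. Mann–Whitney, Kruskal–Wallis/Dunn and the Wilcoxon test are tied to comparisons between groups or cohorts; section 5.5 introduces its tests as examples; none is assigned to change over time. A statistical analysis plan, not shown, may supply a method. Change from a person's own baseline is estimable whatever the lag.

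**Conclusion.** The timing point holds. Section 2.2 contradicts itself on the time origin. Where the 21-day limit applies, the nominal 2-week sample can fall anywhere from day 10 to 35 after onset and the 4-week sample from day 28 to 49 (5–40 and 23–54 with the window). For non-inpatient asymptomatic/mild and recovered participants the lag has no stated bound. The severity contrast and the promised phase analysis can therefore be confounded by time since infection. Direction and size are unknown, because the documents give no lag distribution by group; it would be wrong to conclude that any severity difference found must be an artefact.

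The timing arithmetic rests only on protocol figures. The point about tests is secondary: no paired or repeated-measures method is named. Unpaired tests on paired visits would be conservative and usually less powerful, not biased. The power gap (0.71–0.79 against 0.82–0.99 at n = 50) depends on the assumed shift and correlations.

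**What to change.** 1. Reconcile section 2.2 (rationale and schedule), Table 1 and section 4.5 on one stated time origin. Merely rewording the rationale to refer to baseline would leave the kinetic argument unsupported.
2. Add a CRF date field with its source: symptom onset; first positive test if there were no symptoms; index infection for recovered participants. Allow unknown, which is needed for those classed asymptomatic on nucleocapsid antibody alone.
3. Adjust severity contrasts for days since that date and analyse trajectories against it. Handle unknown-date participants separately in a sensitivity analysis. Keep visit labels for scheduling only.
4. Name a paired or mixed-effects method for visit-to-visit and blood-versus-SWMF comparisons.

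The cost is one field and some wording; no visit moves and no sample is added. The field should be added while dates can still be recovered. The drawback is that the date will be approximate or missing for some asymptomatic cases.

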2.3 Trial Flowchart

[figure not shown]

Table 1 Summary of Groups, Recruitment numbers, screening and sample collection

Patient Categories and timelines

		Baseline Im+Mb	10-14d	4 weeks	12 weeks*
South Asian	SA1 Uninfected	100	-	Im+Mb*	
	SA2 Asymptomatic/mild	100	Im	Im+Mb	Im
	SA3 Moderate/severe	100	Im	Im+Mb	Im
	SA4 Recovered	100		Im+Mb	Im+Mb
White British	WB1 Uninfected	100	-	Im+Mb*	
	WB2 Asymptomatic/mild	100	Im	Im+Mb	Im
	WB3 Moderate/Severe	100	Im	Im+Mb	Im
	WB4 Recovered	100		Im+Mb	Im+Mb
TOTAL	Participants	800	200	400	300
	Immunology samples	800	200	400	300
	Microbiome samples	800	-	400	100
	Blood samples	800	-	400	300

Samples for immunology studies (blood and stimulated whole mouth fluid- (SWMF) and microbiome (SWMF) are taken from all participants at baseline. Sequential samples of SWMF for immunology will be taken at approximately 2, 4 and 12 weeks in the first 50 of the COVID positive groups. Sequential samples for microbiome analysis will be performed on these samples at 4 weeks, and at 12 weeks in the recovered groups. The aim (following statistical advice) is to sample a minimum of 50 participants per group in the cross sectional part of the study, and a minimum of 30 per group in the sequential part.

* Post vaccination sample for subset of 50 two weeks after first and second vaccination.

2.4 Trial Statistics

Statistical advice indicates that with expected variation in both immunological and microbiome parameters, between 30 and 50 values per parameter would be optimal to demonstrate statistical differences on a cross sectional basis (more than 21 for immunological samples, more than 30 for microbiome samples) and that 30-40 per parameter would be optimal on a sequential basis. We

have therefore aimed for a minimum of 50 and a maximum of 100 participants for the cross sectional comparison, and between 30 and 50 participants on a longitudinal basis. Groups of 100 for the cross-sectional part of the study and 50 for the sequential also allow for the unexpected withdrawal of participants and leave sufficient numbers of samples for statistical analysis.

The microbiome, clinical data and immunome data will be associated using Spearman correlations. A Mann–Whitney U-test will be used to determine the median differences of continuous clinical variables. For more than two groups, the Kruskal–Wallis test with post-hoc Dunn test will be used. The association between the prototype prevalence, immunome and clinical data will be modelled with single (univariate) or multiple (multivariate) dependent variables (clinical & immunome metadata features) and will be performed using multinomial or binomial logistic regression.

Standard pipelines and statistical methods already in use within the group will be used for oral metagenome data. The data will be initially quality controlled and trimmed. Human contaminant sequences will be removed from reads by mapping against a human reference genome using Bowtie2. Scaffolds will be assembled from filtered reads using SPAdes. SAMtools will be applied to generate statistics for each filtered scaffold. The scaffolds will be merged to one scaffold file and bacterial genes from the file will be identified using Prodigal. The genes will be clustered and redundant genes will be removed using CD-HIT. Next all the unmapped reads will be mapped to the list of assembled genes and using METEOR software suite the gene counts will be generated for each sample and according to the depth of the sample sequence data, the count table will be downsized. Then the updated count table will be normalized to the gene length and converted to a frequency matrix, which we call the Gene Abundance Matrix.

The gene richness analysis will be done based on the updated count matrix to obtain the diversity of the samples at the gene level. A Wilcoxon test follow by Benjamini-Hochberg multiple testing correction will be used to obtain the significant changes between the cohorts. Next, we will map each sample to our already generated 1,942 oral Metagenomic Species Pangenomes (MSP), as an updated format for the metagenome species. The relative abundance of an MSP will be calculated using the mean abundance of its 100 ‘marker’ genes. To contrast the species abundance in different cohorts, we will perform Benjamini-Hochberg multiple testing correction of a Wilcoxon test. Functional analysis will also be performed using the PFAM and KEGG databases. Antimicrobial resistance analysis will be performed by searching reads using the CARD (Comprehensive Antimicrobial Resistance Database) database. In addition, “ortotyping” will be performed using the microbial information on the genus-level abundance with a Hellinger transformation with a Dirichlet multinomial mixtures (DMM) approach to cluster individual samples to distinct groups based on their microbiome composition, and a Fisher’s exact test will be used to identify the prevalent ortotype.

3. Sample Size, Selection and Withdrawal of Subjects

The success of the national vaccination programme has necessitated casting the recruitment net more widely than originally anticipated. Sample size is discussed in 2.4

Uninfected (vaccinated or unvaccinated) will be identified by advertising within KCL and GSTT sites, and at PIC sites, via social media and by recruitment at vaccination centres at GSTT or

testing centres at KCL/GSTT. Patients admitted to wards for non-COVID reasons and found to be SARS-CoV2 negative will be invited to participate. Uninfected (vaccinated) will be identified by recruitment at vaccination centres and by advertising within KCL and GSTT and PIC sites. Uninfected participants will be further defined as those who do not show antibodies to nuclear capsid protein antigens. The presence of such antibodies would indicate exposure to SARS-CoV2 rather than immunisation, and would be classified as asymptomatic if no history of symptoms.

All will be given the Patient Information Leaflet (PIL) about the study and access to the study website (<https://www.kcl.ac.uk/research/mimsa>)

Asymptomatic/mild subjects will be recruited from those identified as positive for SARS-CoV2 carriage in routine testing at KCL or GSTT. In both cases local staff will inform them about the trial and give out a patient information sheet. A medical history will be taken from those who consent to take part in the research

Symptomatic moderate/severe patients will be recruited within Guys and St Thomas Hospital, mainly in conjunction with the GSTT COVID infection teams. Patients will be recruited from those admitted or planned to be admitted to GSTT with a recent onset (≤ 21 days) of symptoms of COVID-19 and a confirmed positive nasal/nasopharyngeal PCR test for SARS-CoV-2. They will be identified and approached by the clinical staff caring for them on the wards who will discuss the trial in outline and offer the PIL. Should the patient wish to consider participation after reading the PIL, the clinical research dentist (summoned by clinical ward staff) will obtain signatures of consent.

Recovered participants will be patients who have had COVID and fulfil the inclusion criteria. They will have either been discharged from GSTT or be attending either the post-COVID or ICU follow-up outpatient clinics and will be sent letters of invitation to participate. They will also be recruited from participating GP PIC sites, KCL sites and GSTT sites

Number of subjects	Subject selection
Group 1. SA1, BW1 Uninfected Subjects (n=100 each)	Uninfected subjects, both South Asian and White British will be recruited by advertisement within KCL or social media, from non-COVID in-patients or outpatients or attending A&E at GSTT and at SARS-CoV2 antigen testing centres and vaccination centres and at PIC sites. They will be furnished with the participant information leaflet and invited to take part in the study. After obtaining informed consent, oral examination, oral & general health questionnaires and samples of blood and stimulated whole mouth fluid (SWMF) (see below) will be taken either on the wards (inpatients), A&E or at the department of Oral Medicine at Guys Hospital
Group SA1v, BW1v (n=50)	In a subset of uninfected subjects from those attending for vaccination or volunteers, blood and SWMF will be taken 2 weeks after the first vaccination and 2 weeks after the second vaccination for immunology and microbiome analysis.


Group 2. SA2, BW2. Asymptomatic/mild n=100 each
	
Asymptomatic/mild SARS-CoV2 positive group Volunteers or subjects attending SARS-CoV2 testing centres who are found to be antigen positive or In-patients who have positive Covid tests and designated as asymptomatic/mild but admitted for non-covid reasons or those attending A&E with COVID but designated as mild/asymptomatic will be furnished with the participant information leaflet and invited to take part in the study After obtaining informed consent, oral examination, oral health & medical history questionnaires and blood and stimulated whole mouth fluid (SWMF) (see below) will be taken at the department of Oral Medicine at Guys Hospital or on the wards or in A&E at GSTT and KCH. Groups of 100 South Asian and White British participants will be recruited.

Groups 3 SA3, BW3 n=100 each
	
Moderate/Severe Symptomatic patients Patients either seen at GSTT or admitted as in-patients to GSTT or KCH and found to be SARS-CoV2 positive by RT-PCR in nasopharyngeal samples and designated as moderate/severe on the NIH/NIMR COVID severity scale will be furnished with the participant information leaflet and invited to take part in the study and will be enrolled in the study after obtaining written informed consent. After obtaining informed consent, oral examination, oral health & medical history questionnaires and blood and stimulated whole mouth fluid (SWMF) (see below) will be taken at the department of Oral Medicine at Guys Hospital or on the wards or in A&E. Groups of 100 South Asian and White British participants will be recruited.

Groups 4. SA4, BW4 n=100 each
	
'Recovered' patients These will be patients who have had COVID. They may be invited directly to participate by advertising at sites specified above or be attending either the post-COVID or ICU follow-up outpatient clinics. Patients may cover the COVID severity range and include those with a severe/moderate COVID history. Those attending the post-COVID clinic may include those referred in by primary care including those with long-COVID. Covid positive patients discharged from GSTT and fulfilling the inclusion criteria will be sent letters of invitation to participate. This data is available to the COVID clinical research team and participants will be identified with the Clinical Research Dentist.

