5.1 Central/Local Laboratories

Blood samples designated for routine blood tests and glucose will be sent to the hospital blood pathology lab for processing and analysis according to routine processes.

The remaining blood samples will be processed and prepared in the Centre for Host Microbiome laboratory on [name], Guy’s Hospital. Microbial DNA extraction will be performed in these laboratories. Extracted microbial DNA identified by study number only will be sequenced by specialised commercial companies or academic institutions in the UK or non UK.

The salivary microbiome will be analysed on 50-100 patients per group after microbial DNA extraction with standardised protocol, using shotgun metagenomic sequencing on an Illumina NovoSeq generating > 20 million reads/sample. Sequencing will be performed by a commercial provider. Analysis of the sequencing data will be performed at KCL under the supervision of CHMI academics as described in section 2.4. The salivary metabolome will be determined using NMR. The longitudinal immune response and shifts in the oral microbiota will be correlated with COVID-19 severity as well as both COVID-19 and non-COVID-19 oral disease. We will identify significant differences in oral microbiota & immune responses during transition from viral to immunological to post-COVID-19 phases, identifying specific host factors as therapeutic targets.

Salivary secretory IgA antibody assay to study mucosal responses to antigens associated with COVID-19.

SARS is a closely related virus to SARS-CoV2. Several crystal structures have been published that describe how different antigens recognize the SARS spike protein receptor binding domain. These highlighted antigenic regions in the SARS spike protein. Structures are also now available for the homologous SARS-CoV2 spike protein receptor binding domain. The amino acid sequence of the spike protein from SARS & SARS-CoV2 were compared. Major differences were identified and 10 peptides constructed. Three of these have been selected and will be assayed by ELISA along with Capsid antigens obtained commercially. The group has extensive experience with ELISA techniques, and has performed preliminary experiments to verify their use in SWMF. (This kit has been developed and validated in King's College London, and methodology shared with VHS, Chennai for sample testing.)

Blood and SWMF lymphocyte phenotyping

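### Section 2.4 pairs a count model with Hellinger-transformed abundances, so the number and membership of the orotypes are not validly defined

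*Protocol*

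**What the plan says.** Section 2.4 of the protocol plans orotyping (spelled ortotyping there) as an addition to the main microbiome comparisons. It is to be "performed using the microbial information on the genus-level abundance with a Hellinger transformation with a Dirichlet multinomial mixtures (DMM) approach", with the aim "to cluster individual samples to distinct groups based on their microbiome composition". A Fisher's "exact test will be used to identify the prevalent ortotype" follows.

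The same section describes the tables available before this step:

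- **Gene table:** after downsizing, "the updated count table will be normalized to the gene length and converted to a frequency matrix, which we call the Gene Abundance Matrix".
- **Species table:** "The relative abundance of an MSP will be calculated using the mean abundance of its 100" marker genes.
- **Counts:** the only analysis assigned to them is richness: "The gene richness analysis will be done based on the updated count matrix".

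Nothing in the section gives the DMM a count table, gives the Hellinger step a separate purpose, or states a rescaling to integers. Section 2.4 also plans binomial or multinomial logistic models of the prevalence of something it calls a prototype, which may be the orotype under another spelling.

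**The concern.** The DMM describes how reads fall into categories. For each sample it takes a vector of integers, and the total of that vector tells the model how much sampling noise to expect. The Hellinger transformation divides by the total and takes square roots. The results are non-integers between 0 and 1, and the depth is gone. A model that reads noise from the total is then given a total with no meaning.

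At stake is whether the orotypes reflect structure in the samples or the scale on which the values were entered. Fisher's exact test takes the assigned types as given, so it cannot reveal an error in their number or membership.

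**Working it through.** The protocol gives no figure for this step, so there is none to reproduce. The check is one bound and two simulations.

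**1. Bound on the row total.** Let p_i be a sample's proportions over G genera, summing to 1. The Hellinger values are √p_i. By Cauchy–Schwarz, Σ√p_i ≤ √(G × Σp_i) = √G. That is 6.3 for G = 40, 7.7 for G = 60 and 10 for G = 100. The maximum needs perfectly even genera. The number of genera is an assumption, since the protocol gives none.

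**2. Why the total matters.** With total N and Dirichlet precision A, the variance of an observed proportion with mean m is m(1−m)/n_eff, where n_eff = N(1+A)/(N+A). Take A = 30 (assumed):

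- N = 10,000: n_eff = 10,000 × 31/10,030 = 30.9.
- N = 4: n_eff = 4 × 31/34 = 3.6.

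The model would credit each sample with roughly one eighth of the information. Differences between types then fall within the noise it expects.

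**3. First simulation.** Assumptions: 200 samples, 60 genera, 3 true types, 20,000 reads per sample, 6 data sets, 1 to 4 types allowed, number chosen by BIC.

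- Counts: 3 types in 6/6, adjusted Rand index 1.0.
- Raw Hellinger values: 1 type in 6/6, and index 0.0 when forced to 3. Mean row totals were 4.5 to 5.2.

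**4. Second simulation.** Assumptions: 400 samples, within-type precision 30, about 10,000 genus-level counts per sample, number of types chosen by BIC. The 400 follows from section 2.2, which sends the first 50 in each group to microbiome analysis, and 50 × 8 groups = 400. (Table 1 lists 800 baseline microbiome samples.) Up to 4 types were allowed in the three-type sets and up to 5 in the sets with no types.

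| Input to the DMM | Row total | 3 true types, 40 genera (4 sets) | No types, 40 genera (15 sets) | No types, 100 genera (15 sets) |
|---|---|---|---|---|
| Counts | about 10,000 | 3 in 4/4, index 0.96–1.00 | 1 in 15/15 | 1 in 15/15 |
| Raw Hellinger | 3.4–4.9 | 1 in 4/4; index 0.00 when forced to 3 | 1 in 15/15 | 1 in 15/15 |
| × 100, rounded | 340–495 | 3 in 4/4, index 0.93–0.99 | 1 in 15/15 | 1 in 15/15 |
| × 10,000, rounded | about 34,000–49,500 | 3 in 3/4 (0.93–0.99); 4 in 1/4 (0.78) | 2–5 in 15/15 | 1 in 15/15 |
| × 1,000,000, rounded | about 3.7–4.9 million | not run | 2–5 in 15/15 | 2–3 in 10/15 |

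Raw values lost the true types in all 6 + 4 = 10 data sets. Rescaled values mostly kept them, but whether false types appeared depended on the multiplier and the number of genera. Counts gave the right number of types in all 6 + 4 + 30 = 40 data sets.

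**The case against.** The strongest reply is that the sentence is loose rather than wrong. It may mean a Hellinger step for ordination and a DMM on counts. Section 2.4 says the group will use methods it already runs, so a working implementation probably exists. Software that insists on integers would stop visibly rather than mislead, and the exact input could be left to an analysis plan. This stands in part: the intention may be sound, and a clarification may be all that is needed. But the section does not leave the step open. It names the abundances, the transformation and the model in one chain, and no other sentence supplies counts. An analysis plan that followed it faithfully would carry the mismatch forward.

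Four stronger readings are tempting, and the documents do not support them.

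- **True clusters will be lost and the orotype analyses will fail.** This holds only for raw values. The protocol neither states nor rules out rescaling. With a multiplier of 100 the true types were recovered in 4/4 sets with no false types in 30/30. At larger multipliers the risk reverses to false or extra types.
- **More than 20 million reads are treated as a handful.** The figure in section 5.1 ("generating > 20 million reads/sample") is raw sequencing output, before trimming, removal of human reads and downsizing. It is not a genus-level total. Information in an overdispersed model also levels off near A + 1 (31 here), so the loss is real but not million-fold.
- **The logistic models are invalidated.** That depends on reading prototype as orotype, which is plausible but not stated.
- **The needed counts already exist.** The section yields gene counts and species relative abundances, not a genus-level count table.

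**Conclusion.** The point holds as a mismatch of model and data that the protocol states itself. Read as one chain, section 2.4 does not validly define the number or membership of the orotypes. With raw Hellinger values, true types collapse to one. With rescaled values, the number of types depends on a multiplier that the protocol does not fix.

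The reach is limited. Fisher's exact test on orotypes is affected, and so are the logistic models if prototype means orotype. The richness comparison, the species-level Wilcoxon tests with Benjamini–Hochberg correction and the immunology comparisons do not use these clusters. This should be corrected, but it does not threaten the study's main comparisons.

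The bound √G is exact. The simulation results rest on assumed numbers of genera, depth, precision and separation, on BIC rather than the Laplace approximation, and on only ten data sets with true types (six and four).

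**What to change.** Reword the orotyping sentence in section 2.4 to say that:

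- the DMM is fitted to untransformed genus-level integer counts;
- these counts are aggregated from the downsized count table by a stated rule, before length normalisation and conversion to frequencies (for example, the marker-gene counts of each MSP summed to genus);
- the number of types is chosen by the Laplace approximation or BIC;
- the Hellinger transformation is used only for ordination or distance-based clustering.

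Use one term throughout for orotype, so that it is clear whether the logistic models use these clusters.

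The cost is one added aggregation step and a short text change. The aggregation rule needs some thought, because counts summed before length normalisation also reflect gene length and the number of genes contributing to each genus. No new samples or sequencing are needed.
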